6.10.6. Pharmacokinetic (PK) Studies

As resources permit, stored plasma samples and dried blood spots on filter paper will be available for measuring DHA and piperaquine levels in a subset of patients who are randomized to receive DP. PK studies will be done at UCSF as the capacity for performing these assays does not exist in Uganda.

6.11. Co-enrollment Guidelines

The pregnant women and children from this study may be co-enrolled in observational studies. They may not be co-enrolled in protocols that utilize concomitant study medications. Co-enrollment in other studies will be determined on a case-by-case basis by the protocol team.

6.12. Management of Adverse Events Potentially Related to Study Drugs

The following section outlines management of adverse events potentially related to study drugs (SP or DP). Given the double blinded nature of the intervention, study clinicians and study participants will not be aware of what study drugs are being administered. Therefore all study participants will be considered potentially exposed to either study drug during the period study drugs are first given up to one month after the last dose of study drug is given.

6.13. Grade 1 or 2 Adverse Events

Participants who develop grade 1 or 2 adverse events may continue study drugs. The study clinicians will manage the grade 1 or 2 events according to standard practice.

6.14. Grade 3 or 4 Adverse Events

Management will be as follows:

- Repeat observation or lab test within 72 hours of observation or of receiving lab results report.
- For grade 3 or non-life threatening grade 4 adverse events, subjects may continue taking study drugs pending clinic visit or repeat laboratory tests. Clinician has the option of immediately stopping the study drugs if subject cannot be examined in clinic, if a repeat laboratory test cannot be performed within 72 hours, or if the clinician determines that the continuation of study drugs is unsafe while awaiting clinic exam or test results.
- For grade 4 life-threatening adverse events, study clinicians should hold study drugs pending laboratory confirmation.
- Work-up to exclude other causes.
- For all grade 3 or 4 adverse events supported by repeat clinical exam or laboratory test results, study drugs will be held, and laboratory tests will be repeated every 1-2 weeks, until the adverse event resolves to \leq grade 2 unless there is strong evidence that the adverse event is not related to either study drug.
- If the adverse event persists at grade 3 or 4 for more than 28 days or recurs on re-challenge, and the adverse event is thought to be possibly related to one of the study drugs, the study drugs will be permanently discontinued.

In the event that study drugs are permanently discontinued, study participants will remain in the study, following our intention-to-treat analysis approach. In the event that study drugs are permanently discontinued, study clinicians may become un-blinded to the study participant assigned treatment regimen if this knowledge may assist in the management of the grade 3 or 4 adverse event(s) that lead to the permanent discontinuation of the study drugs.

7. MONITORING OF ADVERSE EVENTS AND MANAGEMENT

7.1. Monitoring and Reporting of Adverse Events

7.1.1. Definitions

An adverse event is defined as "any untoward medical occurrence in a patient or clinical investigation subject administered a pharmaceutical product that does not necessarily have a causal relationship with this treatment" (ICH Guidelines E2A). An adverse event can further be broadly defined as any untoward deviation from baseline health, which includes:

- Worsening of conditions present at the onset of the study
- Deterioration due to the primary disease
- Intercurrent illness
- Events related or possibly related to concomitant medications

(International Centers for Tropical Disease Research Network Investigator Manual, Monitoring and Reporting Adverse Events, 2003).

7.1.2. Identification of Adverse Events

At each scheduled and unscheduled visit to the clinic, study clinicians will assess patients according to a standardized case record form. A severity grading scale, based on toxicity grading scales developed by the NIH Divisions of AIDS (DAIDS) and the Division of Microbiology and Infectious Diseases (DMID) Pediatric Toxicity Tables, will be used to grade severity of all symptoms, physical exam findings, and laboratory results (Appendix J). All participants, regardless of treatment arm, will be assessed using the same standardized case record form. Adverse event monitoring will occur during the period when study drugs are given and up to 1 month after cessation of study drugs.

Data will be captured on the incidence of all adverse events, regardless of severity. For each adverse event identified and graded as severe or life threatening and felt to be possibly, probably or definitely related to study drugs, an adverse event report form will be completed. In addition, an adverse event form will be completed for all serious adverse events and unexpected events, regardless of severity. An adverse event report form will not be completed for events classified as mild or moderate (unless they are serious or unexpected), as mild and moderate symptoms are common and difficult to distinguish from signs and symptoms due to malaria and other common illnesses. The following information will be recorded for all adverse experiences that are reported:

- 1) Description of event
- 2) Date of event onset
- 3) Date event reported
- 4) Maximum severity of the event
- 5) Maximum suspected relationship of the event to study drugs (either SP or DP)

- 6) Whether the event is a serious adverse event
- 7) Initials of the person reporting the event
- 8) Outcome
- 9) Date event resolved

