4.4. Study Enrollment Procedures and Baseline Evaluation

Informed consent will be obtained from women who pass initial screening. Study physicians will conduct the informed consent discussion in the study clinic. Informed consent will include both participation of the pregnant woman and her unborn child (or children in the case of non-singleton pregnancies). Informed consent will be conducted in the appropriate language and a translator will be used if necessary. The study will be described and consent obtained in one of 5 languages (Dopadhola, Ateso, Swahili, Luganda, or English). The consent forms will be translated into each language and back-translated into English to check for any loss or change of meaning. Following the informed consent discussion, pregnant women will be asked by the study physicians to sign a written consent form approved by the UCSF Committee for Human Research (UCSF CHR), Makerere University School of Medicine - Research and Ethics Committee (SOM-REC) or Makerere University School of Biomedical Sciences - Research and Ethics Committee (SBS-REC), and the Uganda National Council for Science and Technology (UNCST) for their own participation in the research study and a second approved consent form for the future use of biological specimens obtained during the course of the study. If the pregnant woman is unable to read or write, their fingerprint will substitute for a signature, and a signature from an impartial witness to the informed consent procedures will be obtained.

Women will be enrolled in study on the same day that they provide informed consent for participation in the research study. On the day of enrollment, women will undergo a standardized history and physical examination, and have blood collected by venipuncture (15 cc's) for filter paper sample (for future molecular studies), routine baseline laboratory testing and storage. Routine baseline laboratory testing will consist of a CBC and ALT measurement. Women who have history of fever in the previous 24 hours or a temperature $\geq 38.0^{\circ}\text{C}$ (tympanic) will have a thick blood smear read urgently in the study clinic. Women with history of fever in the previous 24 hours or a temperature $\geq 38.0^{\circ}\text{C}$ (tympanic) and a positive blood smear will be diagnosed with malaria and treated as described in section 6.2. At the end of the enrolment visit all study participants will be given a long lasting insecticide treated bed net

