6.5. Routine Assessments

Routine assessments will be done in the clinic every 4 weeks for both pregnant women and children. Study participants not seen in the clinic for their every 4 week routine visits will be visited at home and requested to come to the study clinic as soon as possible. Pregnant women and children will receive standards of care as designated in the Uganda MOH guidelines (Appendix G). Routine antenatal care will include screening and treatment for sexually transmitted Infections, blood pressure assessment, urine dipstick for proteinuria, prescription of iron, folate, multivitamins and mebendazole. Routine care in children will include immunizations, vitamin A supplementation, and management of anemia using Integrated Management of Childhood Illness (IMCI) guidelines. During routine assessments subjects will be asked about visits to outside health facilities and the use of any medications outside the study protocol. The study protocol will be reinforced with discussion regarding the need to come to the study clinic promptly upon the onset of any illness and to avoid use of outside medications. Standardized assessment of adherence will also be done for study drugs administered at home and ITN use. A routine history and physical exam will be performed using a standardized clinical assessment form. Blood will be collected by finger prick (in very young children, heel sticks may be substituted for finger pricks) for thick smear, collection of plasma for PK studies, and filter paper samples. If a pregnant woman or parent/guardian of a child reports a fever in the last 24 hours or the patient has a documented temperature $\geq 38.0^{\circ}\text{C}$ tympanic, the patient's thick blood smear will be read immediately and if positive the patient will be diagnosed and treated for malaria (see section 6.2). Phlebotomy for routine laboratory tests (CBC and ALT) to monitor for potential adverse events from study medications and for immunology studies will be performed every 8 weeks in pregnant women and every 16 weeks in children. Screening for non-malaria parasitic infections will be performed once in pregnant women after the 1st trimester at the time routine mebendazole is administered and in children at 1 year of age.

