If the severity of a clinical AE could fall under either one of two grades (e.g., the severity of an AE could be either Grade 2 or Grade 3), select the higher of the two grades for the AE. If a laboratory value that is graded as a multiple of the ULN or LLN falls between two grades, select the higher of the two grades for the AE. For example, Grade 1 is 2.5 x ULN and Grade 2 is 2.6 x ULN for a parameter. If the lab value is 2.53 x ULN (which is between the two grades), the severity of this AE would be Grade 2, the higher of the two grades.

Values Below Grade 1

Any laboratory value that is between either the LLN or ULN and Grade 1 should not be graded.

Determining Severity Grade when Local Laboratory Normal Values Overlap with Grade 1 Ranges

In these situations, the severity grading is based on the ranges in the DAIDS AE Grading Table, even when there is a reference to the local lab LLN.

For example: Phosphate, Serum, Low, Adult and Pediatric > 14 years (Page 20) Grade 1 range is 2.50 mg/dL - < LLN. A particular laboratory's normal range for Phosphate is 2.1 – 3.8 mg/dL. A participant's actual lab value is 2.5. In this case, the value of 2.5 exceeds the LLN for the local lab, but will be graded as Grade 1 per DAIDS AE Grading Table.

II. Definitions of terms used in the Table:

Basic Self-care Functions	Adult Activities such as bathing, dressing, toileting, transfer/movement, continence, and feeding.
	Young Children Activities that are age and culturally appropriate (e.g., feeding self with culturally appropriate eating implement).
LLN	Lower limit of normal
Medical Intervention	Use of pharmacologic or biologic agent(s) for treatment of an AE.
NA	Not Applicable
Operative Intervention	Surgical OR other invasive mechanical procedures.
ULN	Upper limit of normal
Usual Social & Functional Activities	Adult Adaptive tasks and desirable activities, such as going to work, shopping, cooking, use of transportation, pursuing a hobby, etc.
	Young Children Activities that are age and culturally appropriate (e.g., social interactions, play activities, learning tasks, etc.).

PARAMETER	GRADE 1 MILD	GRADE 2 MODERATE	GRADE 3 SEVERE	GRADE 4 POTENTIALLY LIFE-THREATENING
ESTIMATING SEVERITY GRADE				

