Hemoglobin (Hb)	8.5 – 10.0 g/dL	7.5 – 8.4 g/dL	6.50 – 7.4 g/dL	< 6.5 g/dL
Platelets, decreased	100,000 – 124,999/mm ³	50,000 – 99,999/mm ³	25,000 – 49,999/mm ³	< 25,000/mm ³
AST (SGOT)	1.1-<2.0 x ULN	2.0-<3.0 x ULN	3.0-8.0 x ULN	> 8.0 x ULN
Non-routine tests available				
PARAMETER	Grade 1 MILD	Grade 2 MODERATE	Grade 3 SEVERE	Grade 4 LIFE THREATENING
ALT (SGPT)	1.25 – 2.5 x ULN 56 – 113 U/L	2.6 – 5.0 x ULN 114 – 225 U/L	5.1 – 10.0 x ULN 226 – 450 U/L	> 10.0 x ULN > 450 U/L
Bilirubin (Total)	1.1-<1.5 x ULN	1.5-<2.0 x ULN	2.0-3.0 x ULN	> 3.0 x ULN
Creatinine 3 months-2 years	0.6-0.8 x ULN	0.9-1.1 x ULN	1.2-1.5 x ULN	> 1.5 x ULN
Creatinine 2-12 years	0.7-1.0 x ULN	1.1-1.6 x ULN	1.7-2.0 x ULN	> 2.0 x ULN
Hyperglycemia	116 – 159 mg/dL	160 – 249 mg/dL	250 – 500 mg/dL	> 400 mg/dL
Hypoglycemia	55-65 mg/dL	40-54 mg/dL	30-39 mg/dL	<30 mg/dL or abnormal glucose and mental status changes
Potassium, serum, high	5.0 – 5.9 mEq/L	6.0 – 6.4 mEq/L	6.5 – 7.0 mEq/L	> 7.0 mEq/L
Potassium, serum, low	3.0 – 3.5 mEq/L	2.5 – 2.9 mEq/L	2.0 – 2.4 mEq/L	< 2.0 mEq/L
Sodium, serum, high	-	145 – 149 mEq/L	150 – 155 mEq/L	> 155 mEq/L
Sodium, serum, low	-	130 – 135 mEq/L	124 – 129 mEq/L	< 124 mEq/L
Urinalysis				
Hematuria (microscopic)	< 25 RBC/HPF	> 25 RBC/HPF	-	Gross Hematuria
Proteinuria, random collection	1 +	2 +	3 +	4 +

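### Appendix J grades a normal pediatric creatinine as a grade 1-2 adverse event, and the grade 3-4 limits in the same rows need checking

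*Protocol*

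**What the plan says.** Protocol section 7.1.2 applies one scale to every laboratory result: it "will be used to grade severity of all symptoms, physical exam findings, and laboratory results (Appendix J". The creatinine limits in Appendix J, in multiples of the upper limit of normal (ULN), are:

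| Row | Grade 1 | Grade 2 | Grade 3 | Grade 4 |
|---|---|---|---|---|
| 3 months-2 years | 0.6-0.8 | 0.9-1.1 | 1.2-1.5 | >1.5 |
| 2-12 years | 0.7-1.0 | 1.1-1.6 | 1.7-2.0 | >2.0 |
| Adult | 1.1-1.3 | 1.4-1.8 | 1.9-3.4 | ≥3.5 |

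Three instructions at the front of Appendix J bear on how these rows are read:
- Values short of grade 1: "Any laboratory value that is between either the LLN or ULN and Grade 1 should not be graded".
- A result expressed as a multiple of ULN that "falls between two grades, select the higher of the two grades for the AE".
- Local normal values that overlap grade 1: "In these situations, the severity grading is based on the ranges in the DAIDS AE Grading Table".

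Grades are used in three places. Table 8 (section 8.2.2) has an adverse-event outcome stratified by severity. Section 8.5.2 compares rates of grade 3/4 events and SAEs. Section 6.14 states: "For all grade 3 or 4 adverse events supported by repeat clinical exam or laboratory test results, study drugs will be held", with an exception where there is strong evidence that neither study drug is the cause. Under 6.13, grades 1 and 2 require no hold.

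On which tests are routine, section 4.4 says "Routine baseline laboratory testing will consist of a CBC and ALT measurement" and section 6.5 schedules "Phlebotomy for routine laboratory tests (CBC and ALT) to monitor for potential adverse events". Both laboratory tables in Appendix J instead put AST under the routine heading, and ALT and creatinine under "Non-routine tests available".

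**The concern.** A grading scale is meant to pick out departures from normal. Two rows of this one assign grades to results that any laboratory would report as normal. Staff who follow section 7.1.2 to the letter would record a grade 1 or 2 event for a healthy value, and the severity-stratified counts would include events that did not happen.

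The second issue is what the low limits suggest about the rest of the row. If the unit or multiplier is wrong for grades 1 and 2, the same error probably runs through grades 3 and 4. Those grades do have consequences: a hold under 6.14, permanent discontinuation and possible unblinding if the event persists or recurs on re-challenge and is thought possibly related, and entry into the safety comparison of 8.5.2.

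**Working it through.** No sample size, power or error rate is involved, so there is no plan figure to reproduce. The check applies the printed rows to a range of values and reads off the result.

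**Step 1. Grade by value.** Inputs are the three creatinine rows above and the rule that takes the higher grade for a value between two grades.

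| Creatinine (x ULN) | 3 months-2 years | 2-12 years | Adult |
|---|---|---|---|
| 0.5 | none | none | none |
| 0.6 | 1 | none | none |
| 0.7 | 1 | 1 | none |
| 0.85 | 2 | 1 | none |
| 1.0 | 2 | 1 | none |
| 1.1 | 2 | 2 | 1 |
| 1.15 | 3 | 2 | 1 |
| 1.5 | 3 | 2 | 2 |
| 1.51 | 4 | 2 | 2 |

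**Step 2. Highest grade for a value at or below ULN.** Running from 0 to 1.0 x ULN in steps of 0.01 gives a maximum of grade 2 in the younger row and grade 1 in the older row. Under 2 years, every value from 0.6 to 1.0 x ULN carries a grade.

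**Step 3. What a normal value can set off.** Sections 6.14 and 8.5.2 both start at grade 3 (8.5.2 also counts SAEs, which are not defined by grade). The maximum from step 2 is grade 2. A normal creatinine therefore falls under 6.13 and reaches only the all-grade counts.

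**Step 4. Are these rows out of line with their neighbours?** The pediatric table has five rows expressed in multiples of ULN. Grade 1 starts at 1.1 for AST, 1.25 for ALT, 1.1 for total bilirubin, 0.6 for creatinine at 3 months-2 years and 0.7 for creatinine at 2-12 years. Only the two creatinine rows start below 1. The same table has another sign of imperfect checking: hyperglycemia grade 3 is 250-500 mg/dL while grade 4 is >400 mg/dL, so values above 400 and up to 500 carry two grades.

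**Step 5. Do the appendix's own rules remove the problem?** The rule on values short of grade 1 presupposes that grade 1 lies beyond the normal limit; here it lies inside it, so the rule has nothing to act on. The overlap rule deals with a local normal range that happens to cross a fixed cut-off, and it tells staff to follow the table. A limit written as 0.6 x ULN is below ULN in every laboratory, so this rule confirms the faulty reading.

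**Step 6. How often could it occur?** Creatinine is not in the CBC and ALT panel of sections 4.4, 6.5 and 6.10.2. It would be measured only when a physician orders it for another illness (6.10.2). The protocol gives no frequency, so no count can be derived. The 2-12 year row has little reach: dosing ends at week 104 (Appendix D) and adverse-event monitoring ends one month later (7.1.2).

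**Step 7. The AST and ALT headings.** ALT has its own complete row of grades 1-4 in both tables. An ALT result is read from that row whichever heading stands above it, so correcting the heading changes no grade.

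**The case against.** The strongest reply is that the effect is small. Normal creatinine values stay at grade 2 or below, no report form is completed for mild or moderate events unless they are serious or unexpected, the test is discretionary, and assessors are blinded and use one form in all arms. This stands. It limits the size of the problem and leaves no evident route to bias between arms; the likely effect is noise.

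A second reply is that pediatric limits may legitimately differ from adult ones. Appendix J says that separate parameters are given where one set does not suit both populations, and 7.1.2 draws on pediatric tables as well. This also stands in part. That 1.15 x ULN is grade 3 in an infant and grade 1 in an adult does not by itself show the infant limit to be wrong. It does not explain a grade for a value below the upper limit of normal.

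Two stronger readings are tempting and are not supported:
- A reader might infer that a normal creatinine leads to study drug being held. It cannot, because it never reaches grade 3. Even for a raised value, 6.14 requires confirmation on repeat, calls for work-up of other causes, and exempts events with strong evidence of being unrelated.
- A reader might infer that, because AST is labelled routine while ALT is the test drawn, transaminase grades or holds are wrong. They are not. AST and ALT are different analytes with separate rows, different cut-offs between them are no contradiction, and nothing in the protocol lets the heading decide which row applies.

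**Conclusion.** The point holds within limits. A scale that section 7.1.2 makes binding assigns grade 1 or 2 to normal creatinine in children aged 3 months-2 years (0.6 to 1.0 x ULN), and grade 1 to 0.7-1.0 x ULN in the 2-12 year row. The direct effect is confined to all-grade, severity-stratified adverse-event counts, and to children in whom creatinine happens to be ordered; the number cannot be estimated from the protocol.

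Whether the grade 3-4 limits in the same rows are also wrong rests on an assumption: that the sub-ULN limits come from a wrong unit or multiplier. The documents give neither the intended unit nor the local ULN, so a wrong hold or a distorted 8.5.2 statistic is a possibility to rule out and has not been shown. The AST/ALT heading is a labelling inconsistency only. The correction is still worth making, because the table governs safety grading and the cost is low.

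**What to change.** Reconcile the two pediatric creatinine rows, all four grades, with the scale they were taken from and with the adult row. The sponsor's safety team should set the limits; this review does not propose any. Then regrade any stored pediatric creatinine results against the reconciled rows, and check whether any grade 3-4 classification changes.

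As a minor label correction, align the routine and non-routine headings in both Appendix J laboratory tables with sections 4.4, 6.5 and 6.10.2, which name ALT. This changes no grade and no management rule.

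The cost is an appendix correction and a programmed regrade, with no new tests or visits. The downside is that a few events already graded may change grade, and this should be documented.

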8.1.3. Analyses

An intention-to-treat approach to all analyses will be used, including all study participants randomized to therapy and including all follow-up time until the study participants complete the study or early study termination regardless of whether the intervention was stopped due to an adverse event.

Primary analysis. We will compare the prevalence of placental malaria defined by histopathology at birth between the study arms using the Chi-Square test for all pair-wise comparisons. We will explore for any differences of potential confounders between the treatment arms and if necessary adjust our analysis using multivariate logistic regression.

Secondary analyses. We will compare the prevalence of placental parasitemia and our composite birth outcome using the Chi-Square test. We will compare the incidence of maternal malaria and adverse events using Poisson or negative binomial regression models. The Poisson models will include the logarithm of the follow-up time as an offset. We will translate the fitted coefficients and their confidence bounds into percentage effects with the formula $100 * [\exp(\text{coefficient}) - 1]$. This approach is closely related to exponential survival models for analyzing events per follow-up time, but is better able to adjust for violated assumptions. Testing for overdispersion in the Poisson regression can detect violations of these assumptions, and variances can be adjusted accordingly to produce valid p-values and confidence interval. If significant deviations from required distributions in study data are detected, we will employ negative-binomial or zero-inflated negative-binomial models to account for the observed pattern of data. We will compare the prevalence of maternal anemia and asymptomatic parasitemia using generalized estimating equations with adjustments for repeated measures in the same study participant. If necessary, multivariate analyses will be performed to adjust for potential confounders and effect modifiers.

8.2. Hypothesis 2

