8.2.3. Analyses

An intention-to-treat approach to all analyses will be used, including all infants born to mothers assigned to receive IPTp with 3 dose DP or monthly DP and including all follow-up time until the

study participants reach 24 months of age or early study termination regardless of whether the intervention was stopped due to an adverse event.

Primary analysis. We will compare the incidence of malaria using Poisson or negative binomial regression models as described in section 9.1.3. In necessary, multivariate analyses will be performed to adjust for potential confounders and effect modifiers.

Secondary analyses. We will compare the incidence of complicated malaria, hospitalizations, and adverse events using Poisson or negative binomial regression models as described in section 9.1.3. We will compare the prevalence of anemia, asymptomatic parasitemia, and gametocytemia using generalized estimating equations with adjustments for repeated measures in the same study participant. In necessary, multivariate analyses will be performed to adjust for potential confounders and effect modifiers.

8.3. Hypothesis 3

We will test the hypotheses that A) infants born to mothers randomized to receive IPTp with 3 dose DP or monthly DP will have a lower incidence of malaria during the first 24 months of life compared to infants born to mothers who were randomized to receive IPTp with 3 doses of SP, and, B) infants randomized to receive monthly DP between 2-24 months of age will have a lower incidence of malaria between 24-36 months of age after the intervention is stopped compared to infants randomized q 3 monthly DP between 2-24 months of age. For hypothesis 3A, we will only include infants randomized to receive q 3 monthly DP during infancy. For hypothesis 3B, we will also explore for interaction with the intervention given during pregnancy.

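### Read participant by participant, 7.1.2 closes adverse-event capture one month after an early toxicity stop, while the adverse-event rate goes on counting that participant's follow-up time

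*Protocol*

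**What the plan says.** **When AEs are captured.** Protocol 7.1.2: "Adverse event monitoring will occur during the period when study drugs are given and up to 1 month after cessation of study drugs". It does not say whether cessation means the participant's own last dose or the scheduled end of dosing. Section 6.12, on managing AEs, treats participants as potentially exposed "during the period study drugs are first given up to one month after the last dose of study drug is given".

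**What happens after a toxicity stop.** Under 6.14, drug is permanently discontinued for a possibly related event on this condition: "If the adverse event persists at grade 3 or 4 for more than 28 days or recurs on re-challenge". It then says: "In the event that study drugs are permanently discontinued, study participants will remain in the study, following our intention-to-treat analysis approach".

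**What time enters the rate.** For women, 8.1.3 applies intention-to-treat to all analyses, "including all follow-up time until the study participants complete the study or early study termination regardless of whether the intervention was stopped" for an adverse event. It also says: "We will compare the incidence of maternal malaria and adverse events using Poisson or negative binomial regression models", and "The Poisson models will include the logarithm of the follow-up time as an offset". For infants, 8.2.3 counts time until "study participants reach 24 months of age or early study termination regardless of whether the intervention was stopped due to an adverse event". It uses the same models by reference to a section 9.1.3 that does not exist; 8.1.3 is evidently meant. Neither section gives AEs a time at risk of their own.

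**Safety monitoring.** Section 8.5.2 and Table 11 use an incidence rate ratio of grade 3/4 and serious events but do not define its person-time.

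**The concern.** A rate is interpretable only if events can be recorded throughout the time in its denominator. If the 7.1.2 window closes with the individual's last dose, a participant taken off drug contributes one further month of observable time, then time that can only be event-free in the data.

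The closure is also informative. Section 6.14 reserves permanent discontinuation for possibly related grade 3 or 4 events that persist or recur, so the participants whose observation is cut short are those who had the safety outcome. If one regimen causes more such stops, its AE rate falls relative to the other arm's, and an excess of harm is drawn toward the null. AE incidence is a secondary outcome for both women and infants.

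**Working it through.** The protocol states no figure on this point, so there is nothing to reproduce. The calculation shows how large the effect could be in infants, who have the longest follow-up.

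**Inputs from the protocol**
- Infant dosing runs from 8 to 104 weeks of age (5.4, Appendix D); analysed time is T = 2 years (8.2.3).
- Earlier Tororo trial, monthly DP (Table 14): 87 grade 3-4 events at 0.611 per person-year; 3 possibly related grade 3-4 events at 0.021 per person-year. These agree: 87/0.611 = 142.4 person-years, and 3/142.4 = 0.021.

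**Assumptions**
- A 30-day tail after the last dose, full follow-up to 24 months and a constant event rate.
- The share d stopping early is not stated, so a range is used.

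**Unmonitored time L per early stopper**
- Last dose spread evenly over weeks 8 to 104: mean L = 0.85 years; L/T = 0.42.
- Last dose at week 8 (extreme case): L = 2 − 0.153 − 0.082 = 1.76 years; L/T = 0.88.

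**Ceiling on d from the earlier trial.** Dosing lasts 96 weeks, or 1.84 years. The share with at least one possibly related grade 3-4 event is 1 − exp(−0.021 × 1.84) = 3.8%. Permanent discontinuation also requires persistence or recurrence, so at that event rate 3.8% is an upper limit.

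**Effect on the ratio.** Each arm's rate is multiplied by 1 − d × L/T. The rate ratio is multiplied by the quotient of the two factors. For a true ratio of 1.50:

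| Stopping, higher-rate arm vs other | Spread evenly | All at first dose |
|---|---|---|
| 3.8% vs 0% | 1.50 × 0.984 = 1.48 | 1.50 × 0.966 = 1.45 |
| 10% vs 2% | 1.50 × 0.958/0.992 = 1.45 | 1.50 × 0.912/0.982 = 1.39 |
| 20% vs 5% | 1.50 × 0.915/0.979 = 1.40 | 1.50 × 0.824/0.956 = 1.29 |
| 5% vs 5% | 1.50 | 1.50 |

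**Effect on power.** This is an approximate Wald test at two-sided 0.05, with a comparator rate of 0.611 per person-year, 90 infants per arm, 1.9 person-years each and no overdispersion. Power for a true ratio of 1.50 is 89% with matched windows. With evenly spread stopping it is 87% at 3.8% vs 0%, 83% at 10% vs 2%, and 74% at 20% vs 5%.

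**Women.** There is also a gap without any early stop. Take a last course at week 36 and delivery just before week 40. Capture ends near 36.3 + 4.35 = 40.65 weeks, and follow-up ends near 39.9 + 6 = 45.9 weeks. About 5 weeks are counted but not monitored, which is 18-20% of time from a first dose at week 16 or 20. With a week-40 course and delivery soon after, the gap is about 2 weeks. Under Appendix D every arm takes drug or placebo at the same visits, so this gap should be similar across arms. It lowers the absolute rates and largely cancels in the ratio.

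**The case against.** The strongest reply is that 7.1.2 can be read without any conflict. It does not mention early discontinuation, and cessation could mean the scheduled end of dosing. The same section has clinicians assess every participant on one standard form at each scheduled and unscheduled visit, and has all AEs captured regardless of severity. Four-weekly visits and 16-weekly blood tests in children are not tied to drug status, and hospital admissions are a separate infant outcome to 24 months. Section 6.12 concerns management of potentially exposed participants, not when recording ends. So a reader who takes it as settled that capture stops for discontinued participants goes further than the text. What stands is that the text permits that reading, the only parallel window is set by the last dose, and staff could apply the sentence differently.

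A second reply is that AE person-time can be left to the SAP. That holds for the denominator only. A SAP can shorten person-time, but it cannot restore events that were not recorded, and shortening would give up the stated intention-to-treat approach for this outcome.

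A third is that the effect is small. On the protocol's own figures that is right. A single infant stopped at 6 months would have 17 of 24 months (71%) counted without capture, but that figure describes one stopper and not the comparison between arms.

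**Conclusion.** The rules need reconciling. On the per-participant reading, AE capture can close after a toxicity stop while the denominator runs on. The arm with more stops then has its rate understated.

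The likely size is modest: about 1.50 to 1.48 at the earlier trial's related-event rate with stopping spread evenly, and about 1.45 if 10% versus 2% stop. Larger distortions need stopping that is common, early and unequal, and nothing in the protocol indicates this. The constant-rate assumption may be mild, because Table 14 shows 1.159 grade 3-4 events per person-year without chemoprevention against 0.611 on monthly DP. Events after stopping could therefore be more frequent than on drug.

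Two further inferences are not supported:
- **That the Table 11 statistic is biased.** It is affected only if it uses the same person-time, which 8.5.2 does not define.
- **That the women's postpartum gap distorts the comparison.** It is not caused by toxicity and should largely cancel between arms.

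**What to change.** - **7.1.2:** state that AE monitoring runs through the planned dosing period plus one month for every randomised participant, whether or not study drug was stopped early.
- **8.1.3, 8.2.3 and 8.5.2:** define AE person-time so that it matches the capture window.
- **Women:** either extend AE capture to the 6-week postpartum visit, or end AE person-time when capture ends.
- **If capture is left to close after an individual's last dose:** end AE person-time at the same point and label the result an on-treatment rate.

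The cost is a few sentences. Discontinued participants stay in the study, and the four-weekly visits and standard case record form already apply to them. No dosing or discontinuation rule changes.
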